---

## LIST OF ABBREVIATIONS

Abbreviation or special term	Explanation
ABPM	Ambulatory blood pressure monitoring
ADA	Antidrug antibody
AE(s)	Adverse event(s)
AIC	Akaike information criterion
ANCOVA	Analysis of covariance
BMI	Body mass index
BOCF	Baseline-observation-carried-forward
BP	Blood pressure
CI	Confidence interval
COVID-19	Coronavirus disease 2019
CRP	C-reactive protein
CSP	Clinical study protocol
CTMS	Clinical Trial Management System
DCO	Data cut-off
DSIS	Daily Sleep Interference Scale
DSMB	Data and Safety Monitoring Board
DTG	Data transfer guidelines
ECG	Electrocardiogram
eCRF	Electronic case report form
ED50	Half of the E max
ED90	90% of the E max
E max	Maximum response
EOT	End-of-treatment
ePRO	Electronic patient-reported outcome
CCI	
ET	Early termination
FAS	Full analysis set
CCI	
IA	Interim analyses
ICH	International Conference on Harmonization
IERC	Independent Efficacy Review Committee
IP	Investigational product
IPDs	Important protocol deviations

Abbreviation or special term	Explanation
IV	Intravenous
KL	Kellgren and Lawrence
LOCF	Last-observation-carried-forward
LLOQ	Lower limit of quantification
MAR	Missing at random
MCMC	Markov chain Monte Carlo
MCP-Mod	Multiple comparison procedure-modelling
MED	Minimum effective dose
MedDRA	Medical dictionary for regulatory activities
mg	Milligrams
MNAR	Missing not at random
MRI	Magnetic resonance imaging
NGF	Nerve growth factor
NRS	Numerical rating scale
OA	Osteoarthritis
OARSI	Osteoarthritis Research Society International
OMERACT-OARSI	Outcome Measures in Rheumatology-Osteoarthritis Research Society International
PDs	Protocol Deviations
PF	Physical function
PGA	Patient's Global Assessment
PK	Pharmacokinetic(s)
PT	Preferred term
Q2W	Every 2 weeks
RNA	Ribonucleic acid
RPOA	Rapidly Progressive Osteoarthritis
SAE(s)	Serious adverse event(s)
SAF	Safety analyses set
SAP	Statistical analysis plan
SARS-CoV-2	Severe acute respiratory syndrome coronavirus 2
SAS	Survey of Autonomic Symptoms
SAS®	Suite of analytics software
C	
SD	Standard deviation
CCI	
SIF	Subchondral Insufficiency Fracture

Abbreviation or special term	Explanation
SOC	System organ class
TNF	Tumour necrosis factor
WHO	World health organisation
WOMAC	Western Ontario and McMaster Universities Osteoarthritis
CCI	

## AMENDMENT HISTORY

Category*: Change refers to	Date	Description of change	In line with the CSP?	Rationale
Other secondary endpoints	10AUG23	All dosing visits will be used in analysis and summary statistics.	No	Provided the data is available it was decided to analyse it despite the protocol pre-defined timepoints.
Data presentation	15AUG23	The document was updated throughout following the dry run prior to unblinding and final database lock.	Yes/ No	Data presentation was updated to allow more appropriate evaluation of the available data.  In cases where such updates would deviate from the protocol, details are provided in section 6 of this document.
Other	15AUG23	Clarifications added throughout the document.	Yes	To support programming.
Other	12SEP23	Updated references to tables so that numbering aligns.	NA	Not applicable.

\* Pre-specified categories are

Primary or secondary endpoints; Statistical analysis method for the primary or secondary endpoints; Derivation of primary or secondary endpoints; Multiple Testing Procedure; Data presentations; Other

## 1 STUDY DETAILS

This statistical analysis plan (SAP) contains a more detailed description of the final analyses as described in the clinical study protocol (CSP) version 4.0, dated 28th June 2022. The final analyses will be split into two sections:

### **Accelerated final efficacy analysis**

This analysis will be performed once all participants complete or discontinue the treatment period by completing week 12 (EOT/ET) visit. This threshold will indicate a potential data cut-off (DCO) date that will be confirmed by the study team. This confirmed DCO date will be used for analysis purposes and data cleaning will be focused on critical data up to and including the DCO date. Therefore, any data with a date in-between the DCO and database export dates will not be used for accelerated analysis purpose.

The accelerated final efficacy analyses will consist primarily of the primary and secondary statistical analyses and formal statistical testing of the primary endpoint and one key secondary endpoint namely the Change in the WOMAC pain subscale from baseline to Week 12. In addition, the supportive and other statistical analyses of those two endpoints will be executed. Specific outputs that will be produced for this analysis will be summarised in the accelerated final efficacy shells file that will be approved prior to the accelerated final efficacy analysis database lock.

The accelerated final efficacy outputs will be prepared by the blinded IQVIA biostatistics team. The unblinding of the accelerated final efficacy analysis will be done by an independent unblinded IQVIA biostatistics team. The unblinded IQVIA biostatistics team will share the fully unblinded accelerated final efficacy analysis package with AstraZeneca via the restricted EntimICE unblinded folder. More details on the process and preserving the blind can be found in the biostatistical data transfer guidelines (DTG) and the unblinding plan.

### **Final analysis**

This analysis will be performed at the end of the study once all participants either discontinue or complete the whole study including the follow-up period as defined in the clinical study protocol (CSP). This analysis will consist of the statistical analyses and formal statistical testing of the remaining key secondary endpoints and other statistical analyses that were not assessed nor performed during the accelerated final efficacy analysis. Outputs produced for this analysis will be summarised in the study specific shells file that will also include the specification of the outputs produced during the accelerated final efficacy analysis. Those outputs produced for the accelerated final efficacy analysis would be also rerun to ensure that only expected changes occurred (e.g., no ongoing participants in the study, changes associated with post treatment period). If any unexpected changes are observed, then the root cause analyses will be performed.

## 1.1 Study objectives

### 1.1.1 Primary objective

Primary Objective	Estimand description/endpoint

To assess the efficacy of MEDI7352 compared to placebo on chronic pain in participants with painful OA of the knee at Week 12
	
Population:  Adults with moderate-to-severe chronic OA pain of the knee, persistent for 3 months or longer, not adequately controlled by standard-of-care treatments

	
Primary endpoint:  Change in weekly average of daily NRS pain scores from baseline to Week 12

	
Intercurrent events:
 
 
• Discontinuation due to lack of efficacy or an adverse event (AE)
 
• Discontinuation due to other reasons such as loss to follow-up or external circumstances
 
• Taking prohibited pain medication during the treatment period
 
• Taking excessive permitted rescue medication
 

	
Summary measures:
 
 
• Difference in mean changes in weekly average daily NRS pain scores between MEDI7352 doses and placebo
 
• An ‘attributable’ estimand strategy will be adopted for primary endpoint data missing or affected by any of the above intercurrent events: Missing or affected primary endpoint values will be imputed, but the method of imputation will differ depending upon the intercurrent event. Specifically, data missing due to discontinuation, due to lack of efficacy or an AE will be imputed assuming an unfavourable outcome. Similarly, data affected by prohibited or excessive rescue medication will be set to missing and imputed assuming an unfavourable outcome.
 

AE, adverse event; NRS, numerical rating scale; OA, osteoarthritis.

### 1.1.2 Secondary objectives

Secondary Objectives	Estimand descriptions/endpoints

To assess the efficacy of MEDI7352 compared to placebo on additional measures of efficacy in participants with painful OA of the knee
	
Key secondary endpoints:
 
 
• Change in the WOMAC pain subscale from baseline to Week 12
 
• Change in the WOMAC physical function subscale from baseline to Week 12
 
• Change in the PGA of OA from baseline to Week 12
 
 
Other secondary endpoints:
 
 
• Change in the WOMAC pain subscale from baseline to Weeks 2, 4, 6, 8, 10, and 18
 
• Change in the WOMAC physical function subscale from baseline to Weeks 2, 4, 6, 8, 10, and 18
 
• Change in the WOMAC overall scores from baseline to Weeks 2, 4, 6, 8, 10, 12, and 18
 
• Change in the WOMAC stiffness scores from baseline to Weeks 2, 4, 6, 8, 10, 12, and 18
 
• Change in PGA of OA from baseline to Weeks 2, 4, 8, 10, and 18
 
• Percentage of responders as measured by the OARSI responder index using the OMERACT-OARSI definition (Pham et al 2004) at Weeks 2, 4, 8, 12, and 18
 
• Percentage of participants who have achieved an improvement of <math>\geq 2</math> points in PGA of OA at Weeks 2, 4, 8, 12, and 18
 
• Change in the weekly average of daily NRS pain scores from baseline to Weeks 2, 4, 6, 8, 10, and 18
 
• Percentage of participants who have achieved <math>\geq 30\%</math> and <math>\geq 50\%</math> reductions in the weekly average of daily NRS pain scores from baseline to Weeks 2, 4, 8, 12, and 18
 
• Percentage of participants who have achieved <math>\geq 30\%</math> and <math>\geq 50\%</math>, reductions in WOMAC pain subscale scores at Weeks 2, 4, 8, 12, and 18.
 
• Percentage of participants who have achieved <math>\geq 30\%</math> and <math>\geq 50\%</math> reductions in WOMAC physical function subscale at Weeks 2, 4, 8, 12, and 18
 

To assess the PK of MEDI7352 in participants with painful OA of the knee
	
 
• Serum concentration of MEDI7352
 

Secondary Objectives	Estimand descriptions/endpoints
To assess immunogenicity of MEDI7352 in participants with painful OA of the knee	
 
• Presence of ADA to MEDI7352
 
• ADA titre
 

ADA, anti-drug antibody; NRS, numerical rating scale; OA, osteoarthritis; OARSI, Osteoarthritis Research Society International; OMERACT-OARSI, Outcome Measures in Rheumatology-Osteoarthritis Research Society International; PGA, Patient’s Global Assessment; PK, pharmacokinetics; WOMAC, Western Ontario and McMaster Universities Osteoarthritis.

### 1.1.3 Safety objectives

Safety Objectives	Estimand descriptions/endpoints
To assess the safety and tolerability of MEDI7352 compared with placebo in participants with painful OA of the knee	
Safety and tolerability will be evaluated based on AEs, vital signs, and clinical laboratory assessments, including but not limited to:
 
 
• AEs and SAEs
 
• Physical examinations
 
• Neurological examinations
 
• Total Neuropathy Score-nurse
 
• Weight
 
• Vital signs (supine and standing BP, pulse rate, temperature, respiratory rate)
 
• Survey of Autonomic Symptoms
 
• 12-lead ECGs
 
• Clinical laboratory testing (haematology, chemistry, coagulation, and urinalysis)
 
• CRP (inflammatory biomarker)
 
• Concomitant medications and therapies
 
• Injection site reactions
 
• X-ray or/and MRI of large joints a
 

[figure not shown]
a Detailed information about the joints to be evaluated by X-ray and/or MRI as noted in the protocol section 8.2.6 Appendix I.

AE, adverse event; BP, blood pressure; CRP, C-reactive protein; ECG, electrocardiogram; MRI, magnetic resonance imaging; OA, osteoarthritis; SAE, serious adverse event.

#### 1.1.4

CCI

[figure not shown]
CCI

## 1.2 Study design

This is a Phase IIb, multicentre, multinational, randomised, double-blind, placebo-controlled, dose-response study of MEDI7352 in participants 18 to 80 years of age (inclusive) with moderate-to-severe chronic pain of the knee during the previous 3 months or longer, caused by osteoarthritis (OA), not adequately controlled by standard-of-care treatments. See Figure 1 for an overview of the study design. See CSP Table 1 for the schedule of activities planned, including details on the study period.

**Figure 1 Study design**

DSIS, daily sleep interference scores; EOT, end of treatment; IP, investigational product; NRS, numerical rating scale; Q2W, every 2 weeks; CCI

The screening period is up to 45 days; one rescreening attempt is allowed. Pain medication washout is at least 48 hours or 5 half-lives, whichever is longer, prior to the start of the numerical rating scale (NRS) pain score baseline period on Day -7. The baseline NRS pain score period comprises the scores from Day -7 to Day -1 (inclusive).

Visit 3 (Day 7), Visit 9 (Day 74) and Visit 10 (Day 77) may be performed at the participant's home by a qualified health care provider. Visits 9 and 10 cannot be on the same day.

### Treatments and treatment duration:

The study consists of a screening period of up to 45 days (one or more visits), a 12-week double-blind treatment period (10 scheduled visits), and a 24-week follow-up period (3 scheduled visits and 4 phone calls).

After screening and confirmation of eligibility criteria, eligible participants will be randomised on Day 1 at a 1:1:1:1:1 ratio to receive MEDI7352 doses or placebo. Participants will receive a total of 6 CCI injections (every 2 weeks [Q2W] at Day 1, weeks 2, 4, 6, 8 and 10):

- Cohort 1: MEDI7352 CCI
- Cohort 2: MEDI7352 CCI
- Cohort 3: MEDI7352 CCI
- Cohort 4: MEDI7352 CCI
- Cohort 5: Placebo

Participants who complete the treatment period will come in for their end-of-treatment (EOT) visit at Week 12 and then enter the follow-up period. Participants who permanently discontinue investigational product (IP) will be asked to complete study assessments at the early termination (ET) visit (Week 12 assessments) as soon as possible and then enter the follow-up period. All participants are expected to complete the EOT/ET visit and the 24-week follow-up period.

The study incorporates two interim analyses, detailed in section 5.

### 1.3 Number of participants

Approximately 350 eligible participants will be randomly assigned to IPs with one of 4 dose levels of MEDI7352 or placebo. Recruitment will continue until the planned power of the study is achieved (i.e., when statistical information equivalent to 255 participants completing the treatment period is reached) or approximately 350 randomised participants, whichever is sooner (see CSP section 9.2 for more details).

## 2 ANALYSIS SETS

### 2.1 Definition of analysis sets

Details of the analysis sets as described in the CSP are presented in Table 1 below.

**Table 1 Analysis sets**

Analysis set	Definition
Screening set	All participants who provide informed consent and provide demographic and/or baseline screening assessments, regardless of the participant's randomisation and treatment status in the study. This set will be used for participants' disposition.

---

Analysis set	Definition
Full analysis set	All randomised participants. Participants will be analysed according to the intent-to-treat principle whereby their randomised study treatment will be analysed regardless of the study treatment actually received. This set will be used for demographics and other baseline characteristics, medication description and all efficacy analyses.
Safety analysis set	All participants who received at least one dose of double-blind study treatment. Participants will be analysed according to their actual study treatment received, regardless of the randomised study treatment. This set will be used for safety analyses.
PK analysis set	All participants who received at least one dose of double-blind study treatment per the protocol for whom any post-baseline PK data are available and who do not violate or deviate from the protocol in ways that would significantly affect the PK analyses. Participants will be analysed according to their actual study treatment received, regardless of the randomised study treatment.

---

PK, pharmacokinetics.

The assignment of actual treatment if an incorrect IP is administered will follow the below criteria:

- If a participant randomised to placebo receives at least one dose of MEDI7352 XX mg during the entire double-blind treatment period then the actual treatment arm = MEDI7352 XX, where XX corresponds to the lowest dose of MEDI7352 that participant received during the double-blind treatment period.
- If a participant took only MEDI7352 XX mg treatment during the entire double-blind treatment period, then the actual treatment arm = MEDI7352 XX, where XX corresponds to the dose of MEDI7352 that participant took during the entire double-blind treatment period regardless of what treatment participant was randomized to.
- If a participant took a mix of MEDI7352 XX mg treatments during the entire double-blind treatment period, then the actual treatment arm = MEDI7352 XX, where XX corresponds to the lowest dose of MEDI7352 that participant received during the double-blind treatment period regardless of what treatment participant was randomized to.
- If a participant randomised to an active treatment receives only placebo during the entire double-blind treatment period, then the actual treatment arm = Placebo.

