None of the deviations will lead to participants being directly excluded from the analysis sets described in section 2.1. The only exception being for the PK analysis set, if the deviation is considered to significantly impact upon PK assessments. That is:

- If a participant randomised to an active treatment receives only placebo, then such participant would be excluded from the PK analysis set.
- If a participant randomised to placebo receives only active treatment, then such participant would also be excluded from the PK analysis set (per protocol PK samples from participants randomised to placebo are not to be analysed).
- If a participant randomised to placebo receives only placebo, but has any post-baseline PK data available, such participant will be excluded from the PK analysis set.
- If a participant randomised to an active treatment receives an incorrect dose or placebo during the treatment period then such participant would be included in the PK analysis set, but PK assessment(s) after such dose would be excluded from summary outputs.
- Participants with missed IP dose will be included in the PK analysis set, but such participants will be discussed case by case prior to unblinding to agree on the PK assessments use. The generic rule would be to not include assessment(s) made after the missed dose in summary outputs. Such data would be set to missing on the ADaM level so that there is traceability (but will be included in the SDTMs).
- Participants that don't receive a full volume of the IP will be included in the PK analysis set if more than 80% of the volume was administered. If less than 80% of the volume was administered, then such cases will be reviewed prior to unblinding and handled case by case.

In addition, if a participant does not receive IP, this would lead to their exclusion from the safety set. A per protocol analysis excluding participants with specific important protocol deviations is not planned.

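### PK samples kept after a later lower-dose error come from the randomised dose but are summarised under the lower-dose arm, because SAP sections 2.1 and 2.2 conflict

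*SAP*

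**What the plan says.** Four places in the SAP bear on this.

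- **Section 2.1, rules below Table 1.** A participant given more than one active dose is assigned to an arm "where XX corresponds to the lowest dose of MEDI7352 that participant received during the double-blind treatment period". The rule applies whatever the randomised arm.
- **Table 1.** The safety and PK sets carry the same grouping sentence: "Participants will be analysed according to their actual study treatment received, regardless of the randomised study treatment". Efficacy is different. In the full analysis set, "their randomised study treatment will be analysed regardless of the study treatment actually received".
- **Section 2.2, PK rules.** A participant randomised to active treatment who receives an incorrect dose or placebo "would be included in the PK analysis set, but PK assessment(s) after such dose would be excluded from summary outputs". For the placebo arm, "per protocol PK samples from participants randomised to placebo are not to be analysed".
- **Section 4.2.4.** PK concentrations are summarised by treatment group and timepoint in the PK analysis set, and again by ADA status.

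Section 3.4 adds that samples on dosing days are drawn before the injection.

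**The concern.** The exclusion in section 2.2 is there to keep concentrations from a wrong dose out of the summaries. It works by keeping what was sampled while the participant was still on the randomised dose. The rule in section 2.1 then labels the whole participant with the lowest dose received. When the error is a lower dose, the label comes from an injection whose samples have all been removed, and the samples that remain belong to a different dose.

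At stake is the accuracy of concentration by dose. A low-dose summary would contain concentrations from a higher dose, and the higher-dose summary would lose valid ones. Followed as written, the plan produces this result whenever such a case occurs. The same assignment rule also moves that participant's adverse events to the lower-dose arm, which raises a separate question of convention, taken up below.

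**Working it through.** The plan states no figure on this point, so there is none to reproduce. The check traces the rules and then sizes one case.

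**Rule trace.** Section 1.2 gives six injections. Let dose levels run from 1 (lowest) to 4 (highest), with P for placebo. The arm is the minimum active level received (section 2.1). Samples are kept until the first departure from the randomised dose (section 2.2).

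| Randomised | Injections | Arm under 2.1 | Doses behind kept samples | Label fits the samples? |
|---|---|---|---|---|
| 4 | 4-4-4-1-4-4 | 1 | 4-4-4 | No |
| 4 | 4-4-4-4-4-1 | 1 | 4-4-4-4-4 | No |
| 4 | 1-4-4-4-4-4 | 1 | none | Nothing summarised |
| 1 | 1-1-1-4-1-1 | 1 | 1-1-1 | Yes |
| 1 | 4-1-1-1-1-1 | 1 | none | Nothing summarised |
| 4 | 4-4-P-4-4-4 | 4 | 4-4 | Yes |
| P | P-P-4-P-P-P | 4 | not analysed | Not applicable |

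In general, let the randomised dose be r and the erroneous active dose e, given after at least one correct injection. The kept samples come from r and the label is min(r, e). The two agree when e > r and disagree when e < r. So the conflict runs in one direction only. Because dosing-day samples precede the injection, even the sample drawn on the day of the error reflects the earlier, higher dose.

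**Size of one case.** Inputs:

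- Active doses 7.5, 25, 75 and 150 (Appendix D1; Appendix D4.1 also uses 150 as the maximum).
- About 350 randomised (section 1.3) at 1:1:1:1:1 (section 1.2), so 350/5 = 70 per arm.
- Assumption, not in the SAP: concentrations are proportional to dose.

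If one of n values in a group is R times too large, the geometric mean is multiplied by R^(1/n):

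- 150 labelled as 7.5: R = 150/7.5 = 20, and 20^(1/70) = 1.044, about +4%.
- 150 labelled as 75: R = 150/75 = 2, and 2^(1/70) = 1.010, about +1%.
- Two cases with R = 20: 20^(2/70) = 1.089, about +9%.
- No cases: no shift.

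Section 4.2.4 also calls for the arithmetic mean, which is less robust. In the idealised case where the other 69 values are equal, one R = 20 case gives (69 + 20)/70 = 1.27. All these shifts apply only at timepoints before the error. They would be larger in the ADA subsets, where n is smaller.

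**The case against.** The best defence is that the SAP already protects the PK summaries. Samples after an incorrect dose are removed, placebo-arm samples are not analysed, and Table 1 keeps out of the PK set anyone whose deviation would significantly affect PK. This stands for a participant randomised low and later dosed high: a reader might infer that the low-dose PK summary is contaminated in both directions, and it is not. It does not rescue the other direction, because section 2.2 expressly keeps that participant in the set and Table 1 expressly groups by actual treatment.

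A reader might also infer a 20-fold distortion of the low-dose summary. Twenty is a ratio of doses. Its effect on a geometric mean of about 70 values is about 4%, and only under dose-proportionality.

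The most tempting stronger reading is that the safety tables are wrong. The rule does move the adverse events of a mainly high-dose participant to a lower-dose arm. One event is 1/70 = 1.4 percentage points. With assumed true counts of 3/70 high and 0/70 low, moving one case gives 2/69 (2.9%) against 1/71 (1.4%), and moving two gives 1/68 (1.5%) against 2/72 (2.8%). But these counts are invented for illustration, and each moved case must have both a dosing error and the event. No safety section contradicts the rule. Any single-arm rule misplaces a mixed-dose participant, and a highest-dose rule has the mirror defect, since one high-dose error would move a mainly low-dose participant up. The SAP also lists treatment administration and overdoses (section 4.2.7), AESIs (section 4.2.6.1) and important deviations (section 2.2), so a case can be traced. The MEDI7352 Total column does not change with moves between active arms.

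Nor do the documents support the idea that the rule disturbs the planned dose estimation. The MED, ED50 and ED90 come from the efficacy model, which is analysed as randomised.

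**Conclusion.** The conflict between sections 2.1 and 2.2 is real and confined to PK. For a participant randomised to a higher dose who receives at least one correct injection and later a lower dose in error, the plan as written summarises concentrations under a dose that did not produce them. The reverse error causes no mislabelling.

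The likely size is small. It depends on the number of such participants, which the SAP does not give and which may be zero. One extreme case among about 70 shifts the low-dose geometric mean by about 4% at pre-error timepoints, if PK is dose-proportional. Efficacy results are untouched. The lowest-dose rule for safety is a debatable convention, and the documents do not show it to be an error.

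**What to change.** Add one sentence to section 2.2, with a cross-reference in section 2.1: PK concentrations retained in summary outputs after an incorrect dose are grouped under the dose that produced them, which is the randomised dose, and the lowest-dose assignment does not apply to them. In programming terms this is a separate treatment variable for PK summaries and figures.

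For safety, keep the rule. If wanted, add one sensitivity table of AEs and AESIs that attributes mixed-dose participants to the highest dose received, to be produced only if such participants exist.

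The cost is SAP wording and one derivation, plus one optional table. No analysis set changes and no data collection is affected.
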